5.3.2. Meals and Dietary Restrictions

Patients should arrive at the clinic fasting for assessments and study drug administration as defined in the Schedule of Activities ([Section 1.3](#)). This includes at least an 8-hour fast prior to the visit, during which food and drink is restricted. Water is allowed ad libitum.

On all other days, patients will self-administer the study drug orally once daily in the morning on an empty stomach, after an 8-hour fast.

Patients participating in the PK/PD sub-study at Week 0/Day 1, Week 6, and Week 12 should arrive at the clinic fasting (an 8-hour fast prior to the visit) and restrict food and drink until 2 hours post-dose. Food and drink may resume after this timepoint. Patients participating in the PK/PD sub-study do not need to be fasting for blood collection at 24, 48, or 72 hours post last dose of study drug at Week 12.

5.3.3. Alcohol, Cannabis, and Illicit Drug Use

Patients must agree to not consume > 21 standard drinks per week for males and > 14 standard drinks per week for females. A standard drink is defined as 12 oz (360 ml) beer, 1.5 oz (45 ml) liquor, or 5 oz (150 ml) wine.

Patients must abstain from THC (cannabis) and illicit drug use during study participation.

Patients must abstain from CBD use during study participation. Short term topical CBD use (< 14 days) is acceptable.

5.4. Screen Failures

Screen failures are defined as patients who consent to participate in the clinical study but are not subsequently randomized. A minimal set of screen failure information is required and will be documented to ensure transparent reporting of screen failure patients to meet the Consolidated Standards of Reporting Trials (CONSORT) publishing requirements and to respond to queries from regulatory authorities. Minimal information includes demography, screen failure details, eligibility criteria, and any serious adverse event (SAE).

An otherwise eligible patient who is completing a vaccination series prior to enrollment may have the Screening window extended to allow for vaccination completion; laboratory assessments to confirm eligibility should be repeated if the Screening window has been exceeded. An otherwise eligible patient who screen fails due to SARS-CoV-2 testing or clinical status may re-screen at the discretion of the Investigator once SARS-CoV-2 infection has resolved. Any other requests for re-screening must be discussed with the Sponsor.

6. Study Drug

Study drug is defined as any investigational intervention(s), marketed product(s), or placebo intended to be administered to a study patient according to the study protocol.

6.1. Study Drug(s) Administered

Investigational Medicinal Product	TERN-201 capsules	Placebo-to-match (identical in shape, size, appearance, and color to TERN-201 capsules)
Type	Drug	Drug
Dose Formulation	Capsule	Capsule
Unit Dose Strength(s)	1, 3, or 10 mg per capsule	Matching placebo per capsule
Route of Administration	Oral	Oral
Use	Experimental	Placebo
IMP/NIMP	IMP	IMP
Sourcing	Provided centrally by the Sponsor	Provided centrally by the Sponsor
Packaging and Labeling	Study drug will be provided in a labeled carton that contains HDPE bottle(s). In Part 1, each carton will contain one bottle for 4-week usage. In Part 2, each carton will contain two bottles for 4-week usage. Each bottle will be labeled as required per country requirements.	Study drug will be provided in a labeled carton that contains HDPE bottle(s). In Part 1, each carton will contain one bottle for 4-week usage. In Part 2, each carton will contain two bottles for 4-week usage. Each bottle will be labeled as required per country requirements.

Abbreviations: HDPE = High-density polyethylene; IMP = investigational medicinal product; NIMP = non investigational medicinal product

6.2. Study Drug Administration

Patients will be instructed to take capsules as shown in [Table 1](#).

Table 1 Study Drug by Dose Group

Dose Group	TERN-201 Capsules	Placebo-to-Match
Part 1 – 10 mg	One 10-mg capsule QD	One placebo capsule QD
Part 2 – 4 mg	One 1-mg capsule and one 3 mg capsule QD	Two placebo capsules QD
Part 2 – 20 mg	Two 10-mg capsules QD	Two placebo capsules QD

Abbreviations: QD = once per day

6.3. Preparation/Handling/Storage/Accountability

The Investigator or designee must provide acknowledgement of receipt of each shipment of study drug including appropriate temperature conditions have been maintained during transit for all study drug received and any discrepancies are reported and resolved before use of the study drug.

Only patients enrolled in the study may receive study drug and only authorized site staff may supply or administer study drug. All study drug must be stored in a secure, environmentally controlled, and monitored (manual or automated) area in accordance with the labeled storage conditions with access limited to the Investigator and authorized site staff.

The Investigator, institution, or the head of the medical institution (where applicable) is responsible for study drug accountability, reconciliation, and record maintenance (i.e., receipt, reconciliation, and final disposition records).

Further guidance and information for the final disposition of unused study drugs are provided in the Pharmacy Manual.

6.4. Measures to Minimize Bias: Randomization and Blinding

Patients will be randomized to TERN-201 or placebo using an Interactive Web Response System (IWRS). Before the study is initiated, the log-in information and directions for the IWRS will be provided to each site.

Approximately 80 patients will be enrolled in this study. In Part 1, approximately 30 patients will be randomized at a ratio of 2:1 to receive 10 mg TERN-201 (n = 20) or matching placebo (n = 10). In Part 2, if initiated, approximately 50 patients will be randomized at a ratio of 2:1 to receive 4 mg TERN-201 (n = 20), and/or 20 mg TERN-201 (n = 20), or matching placebo (n = 10). Randomization will be stratified by Screening MRI cT1 values \leq 900 ms versus $>$ 900 ms.

In Part 1 of the study, approximately 12 randomized patients will take part in an intensive PK and PD collection after the first dose and after the last dose of study drug. Randomization will ensure approximately 6 patients in the TERN-201 group and approximately 6 patients in the placebo group are assigned to the PK/PD sub-study. Patients who are not participating in the PK/PD sub-study will have trough PK/PD sampling only.

In Part 2 of the study, approximately 15 randomized patients will take part in an intensive PK and PD collection after the first dose and after the last dose of study drug. Randomization will ensure approximately 6 patients at each TERN-201 dose level and approximately 3 patients in the placebo group are assigned to the PK/PD sub-study. Patients who are not participating in the PK/PD sub-study will have trough PK/PD sampling only.

Investigators, patients, all study personnel, and the Sponsor will remain blinded to each patient's assigned dose group throughout the course of the study, unless otherwise specified in [Section 6.4.1](#). Study drug will be dispensed at the study visits as summarized in Schedule of Activities. Returned study drug should not be re-dispensed to patients.

A planned interim analysis will be conducted after all patients in Part 1 have completed Week 6 assessments, and an administrative interim analysis may be conducted after the completion of Part 1 of the study. For these analyses, the study team will be blinded at the individual patient level, with designated personnel responsible for producing the summary results. The details will be addressed in a separate plan.

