- Change from baseline in NASH and fibrosis biomarkers including cytokeratin-18 (CK-18) (M30 and M65), procollagen III n-terminal propeptide (PIIINP), tissue inhibitor of metalloproteinases-1 (TIMP-1), hyaluronic acid (HA), pro-peptide of type III collagen (PRO-C3), and type III collagen (C3M). Other non-invasive tests for NASH fibrosis may also be assessed including the fibrosis-4 (FIB-4) index, enhanced liver fibrosis (ELF) test, NAFLD fibrosis score (NFS), and PRO-C3/C3M ratio.
- Change from baseline in inflammatory biomarkers including high sensitivity C-reactive protein (hs-CRP), interleukin-6 (IL-6), intercellular adhesion molecule-1 (ICAM-1), and vascular cell adhesion molecule-1 (VCAM-1)
- Change from baseline in estimated glomerular filtration rate (eGFR), urine protein including urine protein-to-creatinine ratio (UPCR), and urine albumin-to-creatinine ratio (UACR)
- Change from baseline in plasma methylamine levels (PD marker of VAP-1/SSAO inhibition)
- Exposure-response and dose-response relationship of TERN-201 over 12 weeks, as applicable
- Exposure-response and dose-response relationship, as applicable, of TERN-201 and baseline patient characteristics such as sVAP-1, BMI, diabetes mellitus, and others

Overall Design:

The study is a multi-center, randomized, double-blind, placebo-controlled, adaptive study.

Approximately 80 clinically or histologically diagnosed adult non-cirrhotic presumed NASH patients who meet study eligibility criteria will be enrolled and randomized at an overall ratio of 2:1 into 3 dose groups and placebo across 2 parts of the study.

Part 1

In Part 1, approximately 30 patients will receive 10 mg TERN-201 (n = 20) or matching placebo (n = 10) orally once daily, for 12 weeks.

In Part 1 of the study, approximately 12 randomized patients will take part in an intensive PK and PD collection after the first dose (Week 0/Day 1), at Week 6, and after the last dose of study drug (Week 12). Randomization will ensure approximately 8 patients in the TERN-201 group and approximately 4 patients in the placebo group are assigned to the PK/PD sub-study. Patients who are not participating in the PK/PD sub-study will have trough PK/PD sampling only.

Part 2 may be enrolled based on an interim analysis, as follows:

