Coagulation ^d	X	X								Specific analytes are listed in Appendix 1 . PT/INR will be tested at Screening, Week 0, and if significant abnormal liver function tests are observed.
Fasting Lipid Profile ^d		X			X		X	X		Specific analytes are listed in Appendix 1 .
Serology	X									Includes HBsAg, anti-HCV, and anti-HIV.

	Screening	Treatment Period ^a						ET ^b	Follow-Up ^c	Notes
Visit	Screening	Week 0	Week 2	Week 4	Week 6	Week 8	Week 12		Week 16	
Study Day	-42 to Day -1	Day 1	15	29	43	57	85		113	Visit windows post-randomization through Week 12: \pm 3 days from the specified study day. Visit window Week 16: 1 week prior/+2 days from the specified study day.
COVID-19 Assessment ^{d,e}	X	X			X		X			Screening and on-study COVID-19 assessments should be conducted in accordance with Appendix 8 .
Serum pregnancy test ^d	X	X		X		X	X	X		WOCBP only.
Serum FSH	X									To confirm postmenopausal status, as outlined in Appendix 7 .
Blood Alcohol Test	X									
Urinalysis ^d	X	X			X		X	X	X	Specific analytes are listed in Appendix 1 . Microscopic examination is required if blood or protein is abnormal.
Urine Drug Screen ^d	X	X		X		X	X	X	X	
Total Urine Collection (PK/PD Sub-Study only)		X			X					Total urine collection from 0-8 hours post dose as specified in Appendix 2 .
Intensive PK and PD Sampling (PK/PD Sub-Study only)		X			X		X			Intensive PK sampling will be performed pre-dose and 0.5, 1, 2, 4, 6, 8 and 24 hours after the first dose of study drug on Week 0/Day 1 and Week 6, and at pre-dose and 0.5, 1, 2, 4, 6, 8, 24, 48 and 72 hours after the last dose of study drug at Week 12. Refer to Appendix 2 for additional detail.

	Screening	Treatment Period ^a						ET ^b	Follow-Up ^c	Notes
Visit	Screening	Week 0	Week 2	Week 4	Week 6	Week 8	Week 12		Week 16	
Study Day	-42 to Day -1	Day 1	15	29	43	57	85		113	Visit windows post-randomization through Week 12: \pm 3 days from the specified study day. Visit window Week 16: 1 week prior/+2 days from the specified study day.
Trough PK and PD Sampling ^d		X	X	X	X	X	X	X		Only one sample will be collected at each visit prior to drug administration on the visit day. Patients discontinuing the study at any time for any reason will have one sample collected at the ET visit. Refer to Appendix 2 for additional detail.
Baseline sVAP-1 ^f		X								
NASH/Fibrosis Biomarkers ^d		X			X		X	X		Includes CK-18 (M30 and M65), PIIINP, TIMP-1, HA, PRO-C3, and C3M.
Inflammation Biomarkers ^d		X	X	X	X	X	X	X		Includes hs-CRP, IL-6, ICAM-1, and VCAM-1.

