7.3. Lost to Follow up

A patient will be considered lost to follow-up if he or she repeatedly fails to return for a scheduled visit and is unable to be contacted by the study site.

The following actions must be taken if a patient fails to return to the clinic for a required study visit:

- The site must attempt to contact the patient and reschedule the missed visit as soon as possible, counsel the patient on the importance of maintaining the assigned visit schedule, and ascertain whether or not the patient wishes to and/or should continue in the study.
- Before a patient is deemed lost to follow up, the Investigator or designee must make every effort to regain contact with the patient (where possible, 3 telephone calls and, if necessary, a certified letter to the patient's last known mailing address or local equivalent methods). These contact attempts should be documented in the patient's medical record.
- Should the patient continue to be unreachable, he/she will be considered to have withdrawn from the study.

Discontinuation of specific sites or of the study as a whole are addressed in [Section 10.1.8](#).

8. Study Assessments and Procedures

Study procedures and their timing are summarized in the Schedule of Activities. Protocol waivers or exemptions are not allowed.

Adherence to the study design requirements, including those specified in the Schedule of Activities, is essential and required for study conduct.

All screening evaluations must be completed and reviewed to confirm that potential patients meet all eligibility criteria. The Investigator will maintain a screening log to record details of all patients screened and to confirm eligibility or record reasons for screening failure, as applicable.

The maximum amount of blood collected from each patient over the duration of the study is not expected to exceed 650 mL. Repeat or unscheduled samples may be taken for safety reasons or for technical issues with the samples.

If a patient requires home quarantine due to SARS-CoV-2 infection or exposure, or due to COVID-19 symptoms or other associated concern with attending an in-person study visit; home health care visits may be conducted to continue study assessments in the patient's home where feasible, and/or remote visits via telephone, telemedicine, or other appropriate virtual communication may be substituted for a visit to the site.

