Appendix 2: Sample Collection for Pharmacokinetics and Pharmacodynamics

[Table 3](#) presents a description of PK/PD sample requirements at each study visit and timepoint.

Table 3 PK/PD Sampling Timepoints

Week	Day	Timepoint
0 ¹	1	
• Pre-dose (All Patients)• Post dose at the following timepoints (PK/PD sub-study only):
○ 30 ± 2 minutes○ 1 hour ± 5 minutes○ 2 hours ± 5 minutes○ 4 hours ± 15 minutes○ 6 hours ± 15 minutes○ 8 hours ± 30 minutes• Total urine collection from 0-8 hours post dose (PK/PD sub-study only)
0	2	
• Post Day 1 dose at the following timepoint (PK/PD sub-study only):
○ 24 hours ± 1 hour
2	15 ± 3	
• Pre-dose (All Patients)
4	29 ± 3	
• Pre-dose (All Patients)
6	43 ± 3	
• Pre-dose (All Patients)• Post dose at the following timepoints (PK/PD sub-study only):
○ 30 ± 2 minutes○ 1 hour ± 5 minutes○ 2 hours ± 5 minutes○ 4 hours ± 15 minutes○ 6 hours ± 15 minutes○ 8 hours ± 30 minutes• Total urine collection from 0-8 hours post dose (PK/PD sub-study only)
6	44	
• Post Week 6 dose at the following timepoint (PK/PD sub-study only):
○ 24 hours ± 1 hour
8	57 ± 3	
• Pre-dose (All Patients)

Week	Day	Timepoint
12	85 ± 3	
• Pre-dose (All Patients)• Post dose at the following timepoints (PK/PD sub-study only):
○ 30 ± 2 minutes○ 1 hour ± 5 minutes○ 2 hours ± 5 minutes○ 4 hours ± 15 minutes○ 6 hours ± 15 minutes○ 8 hours ± 30 minutes
12	86	
• Post Week 12 dose at the following timepoint (PK/PD sub-study only):
○ 24 hours ± 1 hour
12	87	
• Post Week 12 dose at the following timepoint (PK/PD sub-study only):
○ 48 hours ± 2 hours
12	88	
• Post Week 12 dose at the following timepoint (PK/PD sub-study only):
○ 72 hours ± 4 hours
ET	ET	
• At the ET Visit, for all patients discontinuing the study at any time for any reason prior to Week 12

NOTES:

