#### **2.2.4. Treatment Assignment, Blinding, and Randomization Methodology**

Patients will be randomized to TERN-201 or placebo using an Interactive Web Response System (IWRS). Before the study is initiated, the log-in information and directions for the IWRS will be provided to each site.

Up to approximately 80 patients will be enrolled in this study. In Part 1, approximately 30 patients will be randomized at a ratio of 2:1 to receive TERN-201 10 mg (n = 20) or matching

placebo (n = 10). In Part 2, if initiated, up to approximately 50 patients will be randomized at a ratio of 2:1 to receive TERN-201 4 mg (n = 20), and/or 20 mg TERN-201 (n = 20), or matching placebo (n = 10). Randomization will be stratified by Screening MRI cT1 values  $\leq$  900 ms versus  $>$  900 ms.

The randomization codes will be provided to bioanalytics to allow for the exclusion of placebo patients from the PK assay. Bioanalytics will not disclose the randomization code or the results of their measurements until the trial is officially unblinded.

Emergency unblinding procedures are outlined in Section 6.4.1 of the study protocol and in the unblinding plan.

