### 8.7.4. Plasma Pharmacokinetic Parameters

Sparse PK samples may be used to calculate PK parameters using population pharmacokinetic (Pop PK) modeling. Data from the study may be combined with data from other studies for the

purposes of Pop PK modeling. If Pop PK modeling is performed, the process will be described in a separate analysis plan.

For the purposes of this SAP, plasma PK parameters will be computed for the PK/PD sub-study patients only. Plasma PK parameters for TERN-201 and its metabolites (TRN-001021 and TRN-001744) will be calculated from the individual plasma concentrations using a non-compartmental approach for Week 0/Day 1, Week 6, and Week 12. Week 0/Day 1 and Week 6 will include pre dose and all post dose assessments prior to the next dose. Week 12 will include pre dose and all post dose assessments. The actual PK sampling times will be used for the PK analysis. If actual PK sampling times are missing, nominal times will be used. If the 24 hr sample is missing at Week 6 or Week 12, the predose sample concentration may be re-used for the 24 hr sample for the purposes of calculating PK parameters, if appropriate.

**Table 6** presents the plasma PK parameters for TERN-201 and its metabolites (TRN-001021 and TRN-001744) to be calculated.

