#### **8.7.5. Statistical Methods for Pharmacokinetic Parameters**

Plasma PK parameters will be summarized by treatment group using descriptive statistics (number of non-missing observations, arithmetic mean, SD, median, Q1, Q3, minimum, maximum, geometric mean, and geometric CV%).

For the calculation of summary statistics, all NR and not calculated (NC) values in a data series will be set to missing.

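### Protocol 6.4 splits the Part 1 PK/PD sub-study 6:6, while Protocol 1.1, Protocol 4.1 and SAP 2.2 split it 8:4

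*Protocol*

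**What the plan says.** Protocol 6.4 (Measures to Minimize Bias: Randomization and Blinding) says of the Part 1 sub-study: "Randomization will ensure approximately 6 patients in the TERN-201 group and approximately 6 patients in the placebo group". Protocol 1.1 says: "Randomization will ensure approximately 8 patients in the TERN-201 group and approximately 4 patients in the placebo group". Protocol 4.1 and the Part 1 text of SAP 2.2 give the same 8 and 4. All four places put the sub-study at about 12 patients. SAP 2.2.4, the SAP's counterpart to Protocol 6.4, gives no sub-study split.

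The use of these patients is set out in the SAP. Section 8.7.4 states that, for the SAP's purposes, "plasma PK parameters will be computed for the PK/PD sub-study patients only". Section 2.2.4 states: "The randomization codes will be provided to bioanalytics to allow for the exclusion of placebo patients from the PK assay". Section 8.7.5 states: "Plasma PK parameters will be summarized by treatment group using descriptive statistics".

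Two smaller wording points sit nearby. Protocol 6.4 places intensive collection after the first and last doses only, whereas Protocol 1.3 schedules it "after the first dose of study drug on Week 0/Day 1 and Week 6" as well as at Week 12, and Appendix 2 agrees. Protocol 1.1, Protocol 4.1 and SAP 2.2 also give 2:1 as the overall allocation ratio, and Protocol 6.4 and SAP 2.2.4 give 2:1 for Part 2.

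**The concern.** The two splits are in current operative text, and the one that disagrees is in the section an IWRS build would naturally be taken from. A 1:1 target and a 2:1 target are different allocations, even with the word approximately attached.

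The split fixes how many intensive 10 mg profiles exist. Placebo patients contribute none, so each sub-study place moved from TERN-201 to placebo removes one PK profile. These profiles supply the AUC and Cmax estimates at 10 mg. The decision to open a dose up to 20 mg uses Part 1 PK to predict whether AUC and Cmax stay below stated limits.

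**Working it through.** **Inputs.** Part 1 arms are 20 TERN-201 and 10 placebo. Part 2 arms are 20, 20 and 10 (Protocol 1.1, 4.1 and 6.4; SAP 2.2 and 2.2.4). The sub-study totals are 12 in Part 1 and 15 in Part 2. The Part 2 split is 6 per dose and 3 placebo wherever it is given.

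**1. Do the splits reproduce the stated totals?** 6 + 6 = 12 and 8 + 4 = 12. Part 2: 6 + 6 + 3 = 15. Both Part 1 splits reproduce the total, so it cannot decide between them.

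**2. Fraction of each arm sampled.**

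| Split | TERN-201 | Placebo | Ratio |
|---|---|---|---|
| Part 1, 8:4 | 8/20 = 40% | 4/10 = 40% | 2:1 |
| Part 1, 6:6 | 6/20 = 30% | 6/10 = 60% | 1:1 |
| Part 2, 6:6:3 | 6/20 = 30% per dose | 3/10 = 30% | 2:2:1 |

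Only 8:4 follows the Part 1 allocation and the proportional pattern used in Part 2.

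**3. Intensive 10 mg profiles.** These number 6 under Protocol 6.4 and 8 elsewhere, a loss of (8 − 6)/8 = 25%. For a given between-patient SD, the standard error of a mean PK parameter would be sqrt(8/6) = 1.15 times as large.

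**4. Sub-study PD contrasts (SAP 8.8.4.3).** The SE factor is sqrt(1/n1 + 1/n2), taking equal variances and ignoring the baseline covariate.
- Part 1 alone: sqrt(1/6 + 1/6) = 0.577 under 6:6, against sqrt(1/8 + 1/4) = 0.612 under 8:4. 6:6 is about 6% smaller.
- Both Part 2 doses open and placebo is pooled (SAP 4.6), giving 6 + 3 = 9 or 4 + 3 = 7 placebo. For 10 mg against placebo: sqrt(1/6 + 1/9) = 0.527 under 6:6, against sqrt(1/8 + 1/7) = 0.518 under 8:4. 6:6 is about 2% larger.
- Same setting, each Part 2 dose against placebo: sqrt(1/6 + 1/9) = 0.527, against sqrt(1/6 + 1/7) = 0.556. 6:6 is about 5% smaller.

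The effect on PD precision is small and goes in both directions. It also assumes that these models use sub-study patients only. SAP 8.8.4 says so, but 8.8.4.3 describes the values as pre-dose or trough, which are collected in everyone.

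**5. Allocation ratio (editorial).** N = 20 + 10 + 20 + 20 + 10 = 80, as stated. TERN-201 to placebo is 20:10 = 2:1 in Part 1, 40:10 = 4:1 in Part 2 (2:2:1 by arm) and 60:20 = 3:1 overall. The 2:1 label fits Part 1, and each Part 2 dose against its concurrent placebo. It also fits a trial that opens one Part 2 dose with 10 placebo (40:20), but then N is 60.

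**The case against.** The best reply is that little depends on this. The primary endpoint is safety, and the sample size has no power basis. The secondary PD endpoint is analysed at trough in the full PD Analysis Set (SAP 8.8.3), which the split does not affect. SAP 8.7.4 allows sparse samples to be used for population PK modelling under a separate plan, and all of the roughly 20 patients on 10 mg give trough samples. The counts are approximate and depend on consent to the sub-study. Three of four places agree on 8:4. All of this stands as a limit on the consequence. It does not remove the contradiction, because the place that disagrees is the randomization section. SAP Section 1 says the SAP supersedes the protocol's statistical considerations, but patients are allocated under the protocol, and SAP Section 11 lists no such change.

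A reader might infer that a 6:6 split would undermine the interim dose decision. The documents do not support this: the decision uses whatever Part 1 PK is available, and Protocol 6.4 leaves interim details to a separate plan.

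A reader might also quote a 95% interval about 26% wider with 6 profiles than with 8 (t5/sqrt(6) = 1.049 against t7/sqrt(8) = 0.836). That arithmetic is right, but SAP 8.7.5 plans descriptive statistics and no such interval.

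The Week 6 omission could be read as dropping that collection. It does not, since Protocol Section 8 says: "Adherence to the study design requirements, including those specified in the Schedule of Activities, is essential and required for study conduct". It is a wording gap.

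**Conclusion.** The inconsistency is real and should be corrected, at modest weight. Its one firm size is 6 against 8 intensive 10 mg profiles for the SAP's noncompartmental PK parameters. This rests on the SAP's restriction of those parameters to sub-study patients and on the exclusion of placebo from the PK assay. The evidence favours 8:4 (three places of four, the Part 1 ratio and the Part 2 pattern) but does not prove it, because no passage requires proportional sampling.

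It would be going too far to say that the wrong split was implemented. The documents do not show what the IWRS uses, and sites cannot act on a split by arm because they are blinded and assignment comes from the IWRS. Nor does the overall 2:1 label put the sample size in doubt: the arm sizes are printed consistently and sum to 80, and no analysis uses the ratio.

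**What to change.** 1. Confirm first which Part 1 sub-study split the IWRS specification uses. Editing the text before that could misdescribe what was done.
2. Then reconcile Protocol 6.4 with Protocol 1.1, Protocol 4.1 and SAP 2.2. Use 8:4, unless the sponsor documents that 6:6 was intended and implemented, in which case correct the other three places. State the same split in SAP 2.2.4.
3. In the same edit, as editorial changes only: add Week 6 to the intensive sampling named in Protocol 6.4, and replace the overall 2:1 with the ratios the printed arms give, namely Part 1 2:1, Part 2 2:2:1, and 3:1 overall if both Part 2 doses open.

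The cost is wording in Protocol 1.1, 4.1 and 6.4 and SAP 2.2 and 2.2.4, plus one specification check. No extra patients and no change of analysis method are needed. If the check shows that the IWRS setting itself is not what the sponsor intended, changing it would be additional work.
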